### **8.3.5. Condom use skill behavior assessment**

Assessor ratings of a man's observed use of male and female condoms on male and female genital models will be made.

### **8.3.6. Condom Barriers Scale**

The Condom Barriers Scale (St. Lawrence, Chapdelaine, Devieux et al., 1999) is a 29-item scale with demonstrated reliability and validity. Items are responded to on a 5 point Likert scale from strongly agree to strongly disagree. There are four scales derived from factor analysis; access/availability, partner barriers, effect on sexual experience, and motivational barriers.

### **8.3.7. Bem Sex Role Inventory**

The Bem Sex Role Inventory-Short Form (BSRI; Bem, 1981) will be used to assess levels of adherence to masculine and feminine gender roles (sex roles) among participants. One focus of the intervention is to explore sex roles and sex role stereotyping. In addition

participants are encouraged to adopt an egalitarian approach to negotiating safe sex with their partners. The short form of the BSRI consists of 30 items, which are evaluated on a seven-point Likert scale according to how much the masculine, feminine, and neutral personality characteristics describe the subject. Mean scores ranging from one to seven for feminine, masculine, and neutral gender role orientation are obtained based upon the mean ratings for each category. In the interest of parsimony and reducing response burden, the ten items considered "filler" items, which do not load onto either the masculinity or the femininity scales were eliminated. These items were originally designed to be a measure of social desirability, but did not prove to be an adequate measure of such (Bem, 1981).

### **8.3.8 Biologic Measures**

Urine and alcohol screens will be done at the Baseline assessment to substantiate self-report data. The urine drug screen will occur onsite and test for 10 illicit substances. A breathalyzer will be used to screen for blood alcohol concentration (BAC).

### **8.4. Adverse Event Evaluation**

An adverse event is defined as any reaction, side effect, or untoward event that occurs during the course of the clinical trial. In this study, the only foreseeable intervention-related adverse events are an increase in psychological distress (defined as an increase in depression and/or anxiety symptoms) secondary to focusing on involvement in risk behaviors. Study staff will be trained to provide crisis intervention and referral for clinical emergency situations. The occurrence of AEs will be determined through the use of an AE Worksheet (consisting of one general AE question and a follow up question to gather more information) filled out by the RA at baseline, immediate post treatment, 3 and 6 month follow up assessments. All SAEs will be recorded, respectively, on the AE Case Report Form (CRF) and SAE Form and SAE Summary Report. All adverse events will be recorded on the Adverse Event Forms. See section 9.1.1 for a more through discussion of adverse events monitoring

### **8.5. Treatment Compliance**

The intervention exposure checklist is designed to measure whether the participant has been exposed to the interventions provided in both the intensive gender specific workshop and the standard HIV/AIDS education group. The participant "checks" the interventions he has been exposed to during the assessment period. In addition the participant identifies the source of the exposure.

**Table 3**  
**Schedule of assessment collection**

Assessment Measures	Screening Visit 0	Baseline Visit 1	Post Intervention Visit 2	3 month follow up Visit 3	6 month follow up Visit 4
Addiction Severity Index – Lite (CAB)		X			
Addiction Severity Index- Lite (drug/alcohol only)				X	X
Adverse Events		X	X	X	X
Alcohol Breathalyzer		X			
Bem Sex Role Inventory		X	X	X	X
CIDI		X			
Condom Barriers Scale		X	X	X	X
Condom use skills		X	X	X	X
Demographic	X				
Drug Use Screening <small>(part 2 of Demographics questionnaire)</small>	X				
Inclusion/Exclusion		X			
Injection Risk Assessment (from RBS)				X	X
Intervention Exposure Checklist			X	X	X
Mini-Mental Status Exam	X				
Randomization		X			
RBS (CAB)	X	X			
Sexual Behavior Inventory		X	<small>Most recent sexual event only</small>	X	X
Study Termination Treatment			X		
Study Termination Followup					X

Treatment Session Attendance			X (completed after each treatment session)		
Urine Drug Screen		X			

## 9.0 DATA AND SAFETY MONITORING PLAN

The DSMB convened by CCTN will provide independent oversight monitoring of the trial. SAEs from all the sites will be reviewed by this DSMB. A summary report from the DSMB safety review will be forwarded to the LI, who is responsible for distributing it to all other study investigators, who will in turn submit the summary report to their local IRBs.

THE CCTN DSMB will also periodically monitor the trial as it progresses. Trial performance will be monitored with regards to adequate recruitment and enrollment, integrity of the informed consent process, random assignment to treatment arms, as well as data integrity.

The data and safety monitoring plan consists of three broad components: safety, trial performance and efficacy. In this section we will attend to each of these domains and when appropriate will refer the reader to other sections of the protocol that address these issues in more detail.

### 9.1 Safety

#### 9.1.1. Definition of Adverse and Serious Adverse Events

Adverse events will be categorized as serious or non-serious, as related or not related to the study, and as expected or unexpected. An adverse event is defined as any reaction, side effect, or untoward event that occurs during the course of the clinical trial. Stable chronic conditions, such as drug use, which are present prior to clinical trial entry and do not worsen, are not considered AEs. Common, minor ailments and complaints will be excluded from any type of documentation. These may include: colds, flu's, cuts, scrapes, coughs, headaches, stomach complaints, and general fatigue.

Serious adverse events (SAEs) are defined as any fatal event, any immediately life-threatening event, any permanent or substantially disabling event, any event that requires or prolongs inpatient hospitalization, congenital anomaly or birth defect, or any event requiring intervention to prevent any of the previously listed serious events. Hospital visits that do not result in admittance are not considered SAE's (e.g. emergency room visit for a non study-related injury that does not result in admittance). Normal childbirth and pre-planned elective procedures are not considered SAEs.

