#### 9.1.2. Assessment, Monitoring and Reporting of Adverse and Serious Adverse Events

AE/SAE's will be elicited by research assistants at each assessment visit by asking the participant if he has noticed any new problems or existing problems that have gotten worse

(using the Adverse Events Worksheet). Disclosure of an AE/SAE may also occur in an unsolicited manner to one of the therapists during the treatment. The RA should be focused on gathering data to aid the Study Clinician in determining study relatedness. Assessment of depression must include an assessment of suicidal ideation, as suicidal ideation may require immediate clinical assistance and qualify as an SAE. All clinically significant AEs will be captured on a standardized AE Log, with immediate assessment for whether or not the AE is serious, and whether or not the AE is study-related, in consultation with the site coordinator or Study Clinician (PhD, MD, PI). Study-relatedness will ultimately be determined by the Study Clinician following discussion with the staff member reporting the AE. AEs that are not serious or study related do not require any further paperwork documentation besides the AE Log. In this study, potential adverse events that may be related to the study would be an increase in emotional distress in relation to discussion of past or current HIV risk behaviors or as a result of relationship conflict (i.e. related to the implementation of safe sex practices).

In the case of clinical emergency, staff will be trained to refer participants in such situations to clinical staff in the CTP who will then follow the CTP's policy for managing their clients in crisis.

All study related AEs and SAEs will be followed until resolution. Monitoring and reporting of SAEs will be maintained by the: CTP staff members (e.g. research assistants, therapists, etc.); CTP Site Coordinator; Protocol PI; Study Project Manager; Lead Investigator; and NIDA Medical Monitor.

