Only SAEs and related AEs will be recorded and entered into the study database (via the AE CRF). All SAEs will be recorded on the AE CRF, the SAE Form, and a summary narrative provided via the SAE Summary Report. The AE CRF is a form that will be used to document any adverse event that is thought to be serious or study related. The AE CRF is completed at each assessment point and on an as needed basis. If the adverse event is found to be serious, then a SAE Form and SAE Summary Report must be completed. The SAE Form should be completed by or in consultation with the Study Clinician. The SAE Summary Report contains demographic information and an event narrative and should be completed by the Study Clinician.

[figure not shown]
All SAEs must be reported by fax of the AE CRF, within 24 hours to the Lead Investigator, Protocol PI, Node PI, NIDA Medical Monitor, and to IRBs in accordance with their guidelines. The Study Clinician will be responsible for reviewing the AE CRF and SAE Form, querying the staff as needed, and completing an SAE Summary Report, to be co-signed by the Lead Investigator. Within 14 days the AE CRF and the SAE Form and the signed SAE Case Summary are forwarded to the NIDA Medical Monitor, Protocol PI, and Node PI. At the same time, reports will be submitted to all involved IRBs per reporting requirements.

All study staff – including research assistants, therapists, CTP Site Coordinator, Protocol PI, Lead Investigator, and Study Project Manager-will receive common training for AE and SAE detection, monitoring and reporting. Training will include: definition of AEs; definition and grading of SAEs; indications and procedures for completing the AE log; indications and procedures for completing AE CRFs; indications and procedures for completing SAE Forms and SAE Summary Reports; and procedures for reporting SAEs.

See Figure 3 for the AE/SAE reporting flow chart.

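### The unqualified rule in Section 9.1.1 that hospital visits without admission are not SAEs conflicts with two SAE criteria in the preceding sentence and should be limited to the hospitalization criterion

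*Protocol*

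**What the plan says.** Section 9.1.1 of the protocol defines SAEs by a list of alternatives joined by *or*. The list opens with "any fatal event, any immediately life-threatening event, any permanent or substantially disabling event", continues with inpatient hospitalization and congenital anomaly, and closes with "any event requiring intervention to prevent any of the previously listed serious events". The next sentence reads "Hospital visits that do not result in admittance are not considered SAE's" and gives one example in brackets: an "emergency room visit for a non study-related injury that does not result in admittance".

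On suicidality, Section 9.1.2 (Assessment, Monitoring and Reporting) says that "suicidal ideation may require immediate clinical assistance and qualify as an SAE". It does not mention admission.

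The same section sets what follows from the classification. Clinically significant AEs go on an AE Log and are assessed for seriousness and relatedness. For the rest, "AEs that are not serious or study related do not require any further paperwork documentation besides the AE Log", and "Only SAEs and related AEs will be recorded and entered into the study database". The 24-hour fax, the SAE Form and the SAE Summary Report apply to SAEs. Section 9.0 says that the DSMB reviews SAEs from all sites.

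**The concern.** The exclusion is written as a rule about what is not an SAE. It is not written as a rule about what fails the hospitalization criterion, and it makes no exception for an event that qualifies on another ground. Immediate threat to life and need for preventive intervention can both be present in someone who is treated and sent home the same day. For that person the two sentences give opposite answers.

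At stake is who sees the event and how quickly. SAE status opens the expedited route to the Lead Investigator and the NIDA Medical Monitor, and it is the only event-level DSMB review that the protocol states. Section 5.1 allows up to 7 methadone and 7 drug-free programs (7 + 7 = 14 sites). If some sites follow the list and others follow the exclusion, SAE counts will not be comparable across sites.

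The conflict also touches the harm that the protocol itself foresees. Section 8.4 names increased psychological distress as the only foreseeable intervention-related adverse event.

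**Working it through.** No arithmetic applies: the point depends on no sample size, rate or error level. The check sets the passages side by side and traces one event through them.

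**Step 1. Does each statement depend on admission?**

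| Statement | Section | Depends on admission? |
|---|---|---|
| Immediately life-threatening event is an SAE | 9.1.1 | No |
| Event requiring intervention to prevent a serious event is an SAE | 9.1.1 | No |
| Event requiring or prolonging inpatient hospitalization is an SAE | 9.1.1 | Yes |
| Hospital visit without admission is not an SAE | 9.1.1 | Yes, no exception stated |
| Suicidal ideation may be an SAE | 9.1.2 | No |

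The fourth row agrees with the third. It conflicts with the first two whenever a qualifying event is treated in hospital without admission. It conflicts with the fifth only when the suicidality leads to a hospital visit that ends in discharge.

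**Step 2. Does the bracketed example limit the rule?** It is introduced by *e.g.*, so it illustrates and does not restrict. It also brings relatedness (a non study-related injury) into a rule about seriousness, although the section opens by treating these as separate classifications.

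**Step 3. Trace an immediately life-threatening event, treated and released.**

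| Reading of the exclusion | Judged related? | AE Log | AE CRF and database | 24-hour report, SAE Form, stated DSMB SAE review |
|---|---|---|---|---|
| Literal | No | Yes | No | No |
| Literal | Yes | Yes | Yes, and followed to resolution | No |
| Clarifies hospitalization only | Either | Yes | Yes | Yes |

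Under the literal reading the expedited route is lost whatever the relatedness judgment. Database entry is lost only if the event is also judged unrelated.

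**Step 4. Does anything else settle it?** Section 9.1.2 has seriousness assessed in consultation with the site coordinator or Study Clinician. It reserves the final decision on relatedness to the Study Clinician and says nothing equivalent for seriousness, so the written definition carries the weight. Common training covers the SAE definition, but the definition to be taught is the one with the conflict. The reporting flow chart (Figure 3) was not legible in the text examined, so its triage steps could not be checked.

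**The case against.** The best answer is contextual. The disputed sentence speaks of hospital visits and admittance, which is the vocabulary of the hospitalization criterion alone. The sentence after it, on normal childbirth and planned procedures, also reads naturally as sorting out which hospital contacts count. On that view a visit without admission merely fails one criterion, and a life-threatening event still qualifies under its own. This reading is reasonable and may well be what was meant. It stands as far as showing that the sentence does not plainly override the criteria. It does not remove the defect, because the reader must supply a limit that the sentence does not contain.

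A reader might go further and infer that the exclusion cancels the two criteria, or that a treated-and-released event would never be reported. The documents support neither. The narrower reading is open. Even on the literal one, a clinically significant event is on the AE Log, and a study-related event reaches the AE CRF and the database. Section 8.4 also says that all adverse events are recorded on adverse event forms, although that sits uneasily with the restriction in Section 9.1.2.

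The suicidality argument is also limited. Ideation elicited at an assessment visit is not a hospital visit, so the exclusion does not reach it. The protocol does not discuss an emergency visit for suicidality that ends in discharge; that case is an inference from reading the two sections together.

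Finally, common training could bring all sites to one reading. Its content is not shown, so this is possible but cannot be relied on.

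**Conclusion.** The point holds as an internal conflict in the SAE definition. Section 9.1.1 contains an unqualified exclusion that contradicts two criteria in the sentence before it and fits poorly with the suicidal-ideation statement in Section 9.1.2. A site that follows the exclusion as written would send a life-threatening, treated-and-released event through without expedited SAE reporting or the stated DSMB SAE review. If the site also judged the event unrelated, it would go no further than the AE Log. Sites could classify the same event differently.

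The size cannot be put in numbers. A reader might want a count of men affected. The protocol gives no rate for such events, and a count would also need the share of sites reading the sentence literally and, for database loss, the share of events judged unrelated. The conclusion rests only on the wording. No efficacy analysis is affected. The sponsor should correct this because it governs safety reporting and is cheap to repair.

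**What to change.** Reconcile Sections 9.1.1 and 9.1.2 by limiting the exclusion to the hospitalization criterion. Suggested replacement sentence: *A hospital or emergency room visit that does not result in admission does not by itself meet the hospitalization criterion; the event is still an SAE if it meets any other criterion listed above.* Use the same wording in the common SAE training, so that all sites classify alike.

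This keeps the evident purpose of the present sentence and leaves every listed criterion intact. It concerns event classification and reporting only. The AE Worksheet needs no change: Section 8.4 describes it as a general question with a follow-up, and seriousness is assessed afterwards. The cost is one protocol sentence, a matching change to the training material, a few more SAE forms and a slightly higher SAE count.

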#### 9.1.2. Assessment, Monitoring and Reporting of Adverse and Serious Adverse Events

AE/SAE's will be elicited by research assistants at each assessment visit by asking the participant if he has noticed any new problems or existing problems that have gotten worse

(using the Adverse Events Worksheet). Disclosure of an AE/SAE may also occur in an unsolicited manner to one of the therapists during the treatment. The RA should be focused on gathering data to aid the Study Clinician in determining study relatedness. Assessment of depression must include an assessment of suicidal ideation, as suicidal ideation may require immediate clinical assistance and qualify as an SAE. All clinically significant AEs will be captured on a standardized AE Log, with immediate assessment for whether or not the AE is serious, and whether or not the AE is study-related, in consultation with the site coordinator or Study Clinician (PhD, MD, PI). Study-relatedness will ultimately be determined by the Study Clinician following discussion with the staff member reporting the AE. AEs that are not serious or study related do not require any further paperwork documentation besides the AE Log. In this study, potential adverse events that may be related to the study would be an increase in emotional distress in relation to discussion of past or current HIV risk behaviors or as a result of relationship conflict (i.e. related to the implementation of safe sex practices).

In the case of clinical emergency, staff will be trained to refer participants in such situations to clinical staff in the CTP who will then follow the CTP's policy for managing their clients in crisis.

All study related AEs and SAEs will be followed until resolution. Monitoring and reporting of SAEs will be maintained by the: CTP staff members (e.g. research assistants, therapists, etc.); CTP Site Coordinator; Protocol PI; Study Project Manager; Lead Investigator; and NIDA Medical Monitor.

Only SAEs and related AEs will be recorded and entered into the study database (via the AE CRF). All SAEs will be recorded on the AE CRF, the SAE Form, and a summary narrative provided via the SAE Summary Report. The AE CRF is a form that will be used to document any adverse event that is thought to be serious or study related. The AE CRF is completed at each assessment point and on an as needed basis. If the adverse event is found to be serious, then a SAE Form and SAE Summary Report must be completed. The SAE Form should be completed by or in consultation with the Study Clinician. The SAE Summary Report contains demographic information and an event narrative and should be completed by the Study Clinician.

[figure not shown]
All SAEs must be reported by fax of the AE CRF, within 24 hours to the Lead Investigator, Protocol PI, Node PI, NIDA Medical Monitor, and to IRBs in accordance with their guidelines. The Study Clinician will be responsible for reviewing the AE CRF and SAE Form, querying the staff as needed, and completing an SAE Summary Report, to be co-signed by the Lead Investigator. Within 14 days the AE CRF and the SAE Form and the signed SAE Case Summary are forwarded to the NIDA Medical Monitor, Protocol PI, and Node PI. At the same time, reports will be submitted to all involved IRBs per reporting requirements.

All study staff – including research assistants, therapists, CTP Site Coordinator, Protocol PI, Lead Investigator, and Study Project Manager-will receive common training for AE and SAE detection, monitoring and reporting. Training will include: definition of AEs; definition and grading of SAEs; indications and procedures for completing the AE log; indications and procedures for completing AE CRFs; indications and procedures for completing SAE Forms and SAE Summary Reports; and procedures for reporting SAEs.

See Figure 3 for the AE/SAE reporting flow chart.

**Figure 3: AE/SAE Reporting Flowchart**

### **9.1.2 Human Subject Safety**

Procedures for obtaining written informed consent from participants is provided in section 5.3. The study assessments and interventions consist of techniques that have been widely used in similar forms with comparable populations with minimal problems for the participants. Previous research experience suggests that participants generally perceive these discussions positively. There is, however, some risk that discussing sensitive topics, especially HIV risk behaviors, drug use, sexuality and intimate relationships, will cause distress in some participants. Men may become emotionally fatigued or stressed during the interviews. Yet these risks do not exceed those which are a normal part of any clinical interview or treatment session. The use of individual assessment procedures has not been shown to be either harmful or directly helpful to psychiatric/substance abusing patients. All clinical interviewers and research therapists will be trained to assess for level of distress and will be attentive to patient's needs. Appropriate breaks will be given, and if necessary, additional support at the end of the interview or session.

Participants who do become emotionally stressed will be encouraged to talk to their counselors and raters about their feelings. In the event that any subject is assessed to be in need of extra support, appropriate referrals will be given. At each site, there will be a well-established protocol for crisis intervention for acutely distressed patients. Participants may divulge engagement in HIV risk behaviors that do not generate emotional distress. Since each participant will soon be receiving an HIV prevention intervention as a component of study involvement no immediate intervention is planned unless the participant is continuously placing other identified or unidentified persons at risk for HIV infection. In such cases study staff will follow local reporting and or intervention required in the local community.

Prior to initiating the study, the Lead Investigator will obtain written IRB approval to conduct the study. Should changes to the study protocol become necessary, protocol amendments will be submitted in writing to the IRB by the Lead Investigator for IRB approval prior to implementation. The Washington Node Quality Assurance representatives and local IRB representatives will have access to facilities and records for review and verification of compliance with the IRB approved procedures.

For additional protection of confidentiality, the Washington Node will apply for a NIDA Certificate of Confidentiality once the protocol has received final approval.

All informed consent forms and inclusion/exclusion criteria will be reviewed for all protocol participants. In addition, all research records (case report forms, source documents, etc.) for participants experiencing serious adverse events will be reviewed. Per QAS policy, 100% of the research records for the first 10 participants and a random 10% of the remaining records will be reviewed. In addition, at each monitoring visit to a CTP, the randomization process will be reviewed to ensure that the randomization is occurring according to protocol procedures

